7.4 POST – TREATMENT FOLLOW-UP PHASE

7.4.1 End of Treatment and Early Withdrawal Visit

Patients who completely discontinue study treatment should be scheduled for an End of Treatment (EOT) visit within 15 days following the last dose date of LEE011, at which time all of the assessments listed for the EOT visit will be performed. For details of the assessment, see Table 7-1.

At a minimum, all patients who discontinue study treatment, including those who refuse to return for a final visit, will be contacted for AE evaluations during the 30 days following the last dose date of LEE011.

7.4.1.1 Criteria for Early Withdrawal

Patients may voluntarily withdraw from the study treatment or be dropped from it at the discretion of the investigator at any time. Patients may be withdrawn from the study treatment if any of the following occur:

- Adverse event
- Lost to follow-up
- Physician decision
- Progressive disease
- Protocol deviation
- Study terminated by the sponsor
- Technical problems

7.4.2 Safety Follow-Up

All patients will be followed up for safety up to 30 days after last dose of study drug (LEE011) treatment. Patients whose treatment is interrupted or permanently discontinued due to an AE, including abnormal laboratory value, must be followed until resolution or stabilization of the event, whichever comes first.

7.4.3 Efficacy Follow-Up

Patients who discontinue treatment for reasons other than disease progression, death, start of new anti-neoplastic therapies, lost to follow-up, or withdrawal of consent -- Tumor Assessments and scans (CT or MRI) (See Section 8) must continue to be performed every 8 weeks during the first 12

months, then thereafter, every 3 months (every 12 Weeks) until the start of new anti-cancer therapy, disease progression, death, lost to follow-up, or withdrawn of consent.

7.5 SURVIVAL PHASE

7.5.1 Survival Follow-Up

All patients will be followed for survival status every 12 weeks, starting from the Safety Follow-Up visit, regardless of treatment discontinuation, until death, lost to follow-up, or withdrawal of consent to survival follow-up.

Survival follow-up assessment may be made by a phone call to the patient or designated PHI, EPIC medical record review, or certified mail. At least 3 documented attempts should be made to contact the patient before the patient is considered lost to follow-up.

8.0 MEASUREMENT OF EFFECT

For the purposes of this study, patients will be evaluated for progression every 8 weeks for the first 12 months, then every 12 weeks (3 months) thereafter following the initial chemoembolization. Imaging will consist of a CT or MRI abdomen with liver protocol. The same imaging modality used at baseline will be used for further scans unless documented by primary investigator. CT Chest or additional imaging will be at the discretion of the investigator based on clinical suspicion of additional progressive disease.

8.1 ANTITUMOR EFFECT- SOLID TUMORS

Response and progression will be evaluated in this study using the new international criteria proposed by the Response Evaluation Criteria in Solid Tumors (RECIST) Committee [JNCI 92(3):205-216, 2000]. Changes in only the largest diameter (unidimensional measurement) of the tumor lesions are used in the RECIST criteria. Note: Lesions are either measurable or non-measurable using the criteria provided below. The term “evaluable” in reference to measurability will not be used because it does not provide additional meaning or accuracy.

8.1.1 Disease Parameters

Measurable Disease. Measurable lesions are defined as those that can be accurately measured in at least one dimension (longest diameter to be recorded) as ≥ 20 mm with conventional techniques (CT, MRI, x-ray) or as ≥ 10 mm with spiral CT scan. All tumor measurements must be recorded in millimeters (or decimal fractions of centimeters). A “high-resolution” CT scan is one in which images are recorded at least every 5 mm.

Non-Measurable Disease. All other lesions (or sites of disease), including small lesions (longest diameter <20 mm with conventional techniques or <10 mm using spiral CT scan), are considered non-measurable disease. Bone lesions, leptomeningeal disease, ascites, pleural/pericardial effusions,

lymphangitis cutis/pulmonis, inflammatory breast disease, abdominal masses (not followed by CT or MRI), and cystic lesions are all non-measurable.

Target Lesions. All measurable lesions up to a maximum of 5 lesions per organ and 10 lesions in total, representative of all involved organs, should be identified as **target lesions** and recorded and measured at baseline. Target lesions should be selected on the basis of their size (lesions with the longest diameter) and their suitability for accurate repeated measurements (either by imaging techniques or clinically). A sum of the longest diameter (LD) for all target lesions will be calculated and reported as the baseline sum LD. The baseline sum LD will be used as reference by which to characterize the objective tumor response.

Non-Target Lesions. All other lesions (or sites of disease) that are not target lesions, as defined in the section above, will be identified as non-target lesions and should also be recorded at baseline. Non-target lesions include measurable lesions that exceed the maximum numbers per organ or total of all involved organs as well as non-measurable lesions. Measurements of these lesions are required when feasible, since a patient may have progressive disease on the basis of larger non-target lesions. The presence or absence of each non-target lesion should be noted throughout follow-up.

8.1.2 **Methods for Evaluation of Measurable Disease**

All measurements should be taken and recorded in metric notation using a ruler or calipers. All baseline evaluations should be performed as closely as possible to the beginning of treatment and never more than 28 days before the beginning of the treatment.

The same method of assessment and the same technique should be used to characterize each identified and reported lesion at baseline and during follow-up. Imaging-based evaluation is preferred to evaluation by clinical examination when both methods have been used to assess the antitumor effect of a treatment.

8.1.3 **Response Criteria**

8.1.3.1 **Evaluation of Target Lesions**

Complete Response (CR): Disappearance of all target lesions, determined by two separate observations conducted not less than 4 weeks apart. There can be no appearance of new lesions.

Partial Response (PR): At least a 30% decrease in the sum of the longest diameter (LD) of target lesions, taking as reference the baseline sum LD. There can be no appearance of new lesions.

Progressive Disease (PD): At least a 20% increase in the sum of the LD of target lesions, taking as reference the smallest sum LD recorded since the treatment started, or the appearance of one or more new lesions.

Stable Disease (SD): Neither sufficient shrinkage to qualify for PR nor sufficient increase to qualify for PD, taking as reference the smallest sum LD since the treatment started.

8.1.3.2 Evaluation of Non-Target Lesions

Complete Response (CR): Disappearance of all non-target lesions and normalization of tumor marker level.

Incomplete Response/Stable Disease (SD): Persistence of one or more non-target lesion(s) and/or maintenance of tumor marker level above the normal limits.

Progressive Disease (PD): Appearance of one or more new lesions and/or unequivocal progression of existing non-target lesions

8.1.3.3 Evaluation of Best Overall Response

The best overall response is the best response recorded from the start of the treatment until disease progression/recurrence (taking as reference for progressive disease the smallest measurements recorded since the treatment started). The patient's best response assignment will depend on the achievement of both measurement and confirmation criteria.

Target Lesions	Non-Target Lesions	New Lesions	Overall Response	Best Response for this Category Also Requires:
CR	CR	No	CR	≥4 wks. confirmation
CR	Non-CR/Non-PD	No	PR	≥4 wks. confirmation
PR	Non-PD	No	PR	
SD	Non-PD	No	SD	documented at least once ≥4 wks. from baseline
PD	Any	Yes or No	PD	

Any	PD*	Yes or No	PD	no prior SD, PR or CR
Any	Any	Yes	PD	

* In exceptional circumstances, unequivocal progression in non-target lesions may be accepted as disease progression.
 
Note: Subjects with a global deterioration of health status requiring discontinuation of treatment without objective evidence of disease progression at that time should be reported as “symptomatic deterioration”. Every effort should be made to document the objective progression even after discontinuation of treatment.
				

Note: If subjects respond to treatment and are able to have their disease resected, the patient’s response will be assessed prior to the surgery.

8.1.4 Duration of Response

Duration of overall response: The duration of overall response is measured from the time measurement criteria are met for CR or PR (whichever is first recorded) until the first date that recurrent or progressive disease is objectively documented (taking as reference for progressive disease the smallest measurements recorded since the treatment started).

The duration of overall CR is measured from the time measurement criteria are first met for CR until the first date that recurrent disease is objectively documented.

Duration of stable disease: Stable disease is measured from the start of the treatment until the criteria for progression are met, taking as reference the smallest measurements recorded since the treatment started.

8.1.5 Progression-Free Survival

Progression-free survival (PFS) is defined as the duration of time from start of treatment to time of progression.

8.2 SAFETY/TOLERABILITY

Analyses will be performed for all subjects having received at least one dose of study drug. The study will use the CTCAE version 4.03 for reporting of non-hematologic adverse events (<http://ctep.cancer.gov/reporting/ctc.html>) and modified criteria for hematologic adverse events (Appendix #/letter).

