3.1 ENDPOINTS

Phase Ib:

The primary endpoint of the phase Ib trial will be determination of the maximum tolerated dose of LEE011 administered following chemoembolization (section 6.6).

Phase II:

The primary endpoint of the phase II trial will be progression free survival (PFS) of HCC patients.

Statistics and sample size justification:

PFS is defined to be the time from initiation of treatment to progression or death without evidence of progression. For cases without documentation of progression, follow-up will be censored at the date of last disease assessment without progression, unless death occurs within 4 months following the date of last progression-free, in which case death will be counted as an event. The historical median PFS for TACE alone is 8-10 months. Our institutional median PFS for TACE based on similar chemoembolization procedures as outlined below is 8.0 months. This study will target a hazard ratio of 1.45 with an 80% power and a one-sided significance level of 10%. Assuming a 24-month accrual and an 18-month follow-up period the study requires 40 patients initiating LEE011 treatment with the median PFS for TACE alone is 8 months. PFS will be estimated using the Kaplan-Meier method, and Greenwood's formula will be used to calculate the standard error of the corresponding Kaplan-Meier estimate and 95% confidence interval. Survival curves will be estimated using Kaplan-Meier methodology.

Secondary endpoints of efficacy are to evaluate OS. The same statistical methods used for the analysis of PFS will be used for the analysis of OS.

Other secondary objectives will include description of toxicity of the therapy regimen. These data will be analyzed separately. The safety analyses will be performed on all patients who receive any dose of therapy. Adverse events will be described using the NCI CTCAE v. 4.03 criteria (ctep.cancer.gov/forms/CTCAEv4.pdf). Frequency and severity of adverse events according to the NCI CTCAE v. 4.03 body system and severity criteria will be described. In addition, frequency of Grade 3 or 4 adverse events will be described separately. Causality will also be noted. Adverse events will be recorded for up to 30 days following discontinuation of LEE011 or followed until resolution, whichever comes first. Response rate and toxicity rate will be estimated

using an exact binomial method along with the 95% confidence interval.

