6.2 STUDY TREATMENT

For this study, the term “investigational drug” refers to Novartis study drug LEE011. The procedure, chemoembolization, is standard of care for locally, advanced, non-metastatic HCC. Study treatment in this study refers to the combination of chemoembolization and LEE011.

LEE011 will be supplied by Novartis or its designee as 200 mg hard gelatin capsules as individual patient supply packaged in bottles. Storage conditions are described in the medication label. Chemoembolization will be performed in usual standard of care practice by the interventional radiology division at UT Southwestern Medical Center as described in section 6.12 .

All dosages prescribed and dispensed to the patient, and all dose changes during the study will be recorded in the drug accountability records.

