6.6 DOSE LIMITING TOXICITIES-PHASE IB COMPONENT

The phase Ib component of the study will consist of 3+3 dose escalation rule with the dose of LEE011 escalating up to 600mg daily to determine the maximum tolerated dose (MTD) that will be used during the phase II component. The dose levels for the phase Ib aspect will be 200 mg, 400 mg, or 600 mg daily.

Only the first cycle of therapy (one cycle equals to one month) will be used to determine dose limiting toxicity (DLT). However, if two total grade 5 adverse events or 2 Grade 4 adverse events (lasting ≥ 7 days); occur at any time while the patient is still receiving study treatment that are either: definitely, probably, or possibly related to either LEE011 or TACE the study will be terminated to enrollment.

Only patients started on the first dose of LEE011 will be included in the evaluation of DLT. If a patient has a DLT that patient will not receive further LEE011. Patients following initial chemoembolization who never receive LEE011 will not be included in the MTD analysis and will be replaced. The patients will be followed for thirty days following the initial chemoembolization for safety assessment. Patients will be enrolled into the next highest drug cohort only after 3 or 6 patients have completed the first cycle of therapy. Once the MTD is determined, patients at the MTD dose will continue with LEE011 and represent the first three patients accrued to the phase II aspect.

Due to observed (TACE related, non DLT) toxicity on cohort 1 specific criteria for cohort 1 has been developed after discussion with the FDA. Cohort 1 has been expanded to 6 patients. Decision for dose escalation will be made using the following criteria:

- No or one DLT: the next three patients will be assigned to next higher dose level (400 mg of LEE011).
- At least two toxicities: the MTD is exceeded and the phase I component of the trial will be stopped with no continuation into the phase II component.

For Cohort 2 and 3 the following traditional 3+3 dose escalation rules will be used:

- If a dose limiting toxicity (DLT) is observed in 1 out of 3 patients at a given dose level, up to 3 additional patients will be enrolled and treated at that dose level.
- If 2 out of 3-6 patients at that dose level have DLTs, the dose will be decreased to the previous dose level, and up to 3 additional patients will be enrolled at that dose level for a total of 6 patients.

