 - Physical examination
 - Comprehensive metabolic panel
 - Complete blood count without differential
 - Prothrombin time/INR

At this time the decision will be made to initiate LEE011 treatment.

LEE011 ADMINISTRATION WITH CHEMOEMBOLIZATION

Subjects are to be evaluated from toxicity with:

- Physical Examination (PE)
- Comprehensive Metabolic Panel (CMP)
- CBC
- ECG's

LEE011 will be initiated at the earliest of 7 days following embolization chemoembolization provided the following criteria are met:

- Serum bilirubin elevation $< 2.0 \times \text{ULN}$. If serum bilirubin $\geq 2.0 \times \text{ULN}$ then subjects will be assessed weekly and LEE011 will be initiated once bilirubin $< 2.0 \times \text{ULN}$.
- Resolution of Grade < 3 non-hematologic toxicity (other than bilirubin criteria above). If non-hematologic toxicity \geq Grade 3 then subjects will be assessed weekly and LEE011 will be initiated once $<$ Grade 2;
- Hematological toxicity of \leq Grade 2. If hematologic toxicity \geq Grade 3 then subjects will be assessed weekly and LEE011 will be initiated once \leq Grade 2.

If baseline AST, ALT and alkaline phosphate are elevated post chemoembolization decrease to baseline grade is necessary to continue/initiate LEE011;

- ECOG performance status ≤ 2 ;
- Serum AST, ALT, and/or Alkaline Phosphate $< 5 \times \text{ULN}$.

If criteria is not met, subjects will be reevaluated in 5-7 day intervals. If study subjects are unable to meet the above LEE011 starting criteria following initial chemoembolization treatment within 28 days after treatment, they will be removed from the study.

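### Sections 3.1, 8.2 and 12.1 do not fix one safety set: under 8.2, patients given TACE who never start LEE011 leave the toxicity denominator

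*Combined protocol and SAP*

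**What the plan says.** Three sections describe who enters the safety analysis.

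- Section 8.2 (Safety/Tolerability): "Analyses will be performed for all subjects having received at least one dose of study drug".
- Section 3.1 (Endpoints): "The safety analyses will be performed on all patients who receive any dose of therapy". Section 12.1 repeats this sentence.

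The terms are not interchangeable. Section 6.2 says that the investigational drug "refers to Novartis study drug LEE011", and 7.4.2 uses the label in the same way: "All patients will be followed up for safety up to 30 days after last dose of study drug (LEE011) treatment". For the regimen as a whole, 6.2 has a different term: "Study treatment in this study refers to the combination of chemoembolization and LEE011". The word *therapy*, on which 3.1 and 12.1 rely, is not defined.

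LEE011 starts no sooner than 7 days after TACE, and only if criteria on bilirubin, non-hematologic and hematologic toxicity, liver enzymes and ECOG status are met (section 6.12, under LEE011 Administration with Chemoembolization). Patients "unable to meet the above LEE011 starting criteria following initial chemoembolization treatment within 28 days after treatment, they will be removed from the study".

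For phase Ib, 6.6 adds: "Patients following initial chemoembolization who never receive LEE011 will not be included in the MTD analysis and will be replaced". For phase II, 12.1 counts toward the 40 only patients who have had TACE and started LEE011. Separately, the notes to Table 7.1 allow the first TACE while the RB result is pending. A patient who proves not RB proficient is then taken off as a screen failure.

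**The concern.** The secondary safety objective (2.2.2) is about LEE011 combined with chemoembolization. The stopping rule in 6.6 counts events attributed to LEE011 or to TACE, and cohort 1 was expanded to 6 patients because of TACE-related toxicity. The protocol therefore treats harm after TACE as harm within the trial.

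A safety set that begins at the first LEE011 capsule admits only patients who came through TACE well enough to start. Some of those left out are left out because of what happened to them after TACE, so for that group the exclusion is informative. They are also outside the MTD analysis and outside the phase II 40, so under 8.2 they belong to no analysis set and would appear only in the disposition summary.

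Toxicity is to be reported as an exact binomial rate with a 95% confidence interval (3.1 and 12.1), so the choice of denominator directly changes the reported figure. Leaving it open until the data are in hand allows it to be chosen with knowledge of the result.

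**Working it through.** **Who is in which set**

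| Patient | 8.2 | 3.1 and 12.1, if *therapy* includes TACE | MTD analysis (6.6) | Phase II 40 (12.1) |
|---|---|---|---|---|
| TACE, then LEE011 | in | in | in (phase Ib) | in (phase II) |
| TACE, fails start criteria by day 28 | out | in | out, replaced | out |
| TACE, then found RB-negative | out | in on the wording; no rule stated | out | out |

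**Inputs**

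The plan states no toxicity rate and no non-starter fraction, so it has no figure of its own to reproduce here. The 40 LEE011 starters come from 12.1. Two inputs are assumptions: a 40% event rate among starters (16 of 40), and 5%, 10% or 20% of TACE-treated patients never starting LEE011.

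**Formula**

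Let p be the event rate in starters, q the rate in non-starters, and f the share of TACE-treated patients who never start.

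- Rate under 8.2: p
- Rate over all TACE-treated patients: (1 − f)p + fq
- Difference, all-TACE minus 8.2: f(q − p)

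The number of non-starters beside 40 starters is x = 40f/(1 − f), which gives 2.1, 4.4 and 10 for the three values of f.

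**Results with p = 40%**

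| f | x | 8.2 rate | All-TACE rate, every non-starter has the event: (16 + x)/(40 + x) | All-TACE rate, no non-starter has it: 16/(40 + x) |
|---|---|---|---|---|
| 5% | 2.1 | 40% | 43% | 38% |
| 10% | 4.4 | 40% | 46% | 36% |
| 20% | 10 | 40% | 52% | 32% |

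The last two columns are bounds. As an intermediate case, 10 non-starters of whom 5 have the event give (16 + 5)/50 = 42%, a shift of 2 points. The shift is zero when q = p.

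**Wider range**

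With 40 starters, p from 20% to 50% and 2 to 10 non-starters:

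- If every non-starter has the event, 8.2 understates the combined-regimen rate by 2.4 points (22/42 = 52.4% against 50%) to 16.0 points (18/50 = 36% against 20%).
- If none has it, 8.2 overstates the rate by 1.0 point (8/42 = 19.0% against 20%) to 10.0 points (20/50 = 40% against 50%).

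**Collection window**

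Section 3.1 and the notes to Table 7.1 end adverse-event recording at 30 days after LEE011 stops, or at resolution if sooner. Section 12.1 instead says up to 1 year after discontinuation from study. A phase II patient who never takes LEE011 has no end point under the first rule. Section 6.6 gives a 30-day follow-up after the first TACE, but within the phase Ib text.

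**The case against.** The strongest reply is that there may be no conflict. *Therapy* is undefined, and elsewhere the protocol attaches it to LEE011: in the DLT table of 6.6 and in the 12.1 sentence on who counts toward the 40. In 3.1 the same paragraph ties adverse-event recording to LEE011. All three sections could mean LEE011 starters. That shows an ambiguity, but it does not settle it. Given the definition of study treatment in 6.2, including TACE is the more natural reading, and the sponsor would have to state the narrower one.

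A LEE011-exposed set is also defensible in itself. Someone who had only TACE never received the combination, and TACE is described as standard of care. This stands as a reason to keep the 8.2 analysis as a labelled subset. For LEE011-specific toxicity in exposed patients, 8.2 introduces no bias.

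A reader might infer that 8.2 removes precisely the patients made too ill by TACE and therefore understates toxicity. The documents do not support that much:

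- RB-negative patients given TACE are removed as well, for a reason unrelated to toxicity, as is any other non-starter.
- Failing the start criteria does not require a grade 3 event. LEE011 is withheld at bilirubin of 2.0 × ULN or more, whereas the protocol's grade 2 band runs from 1.5 to 3.0 × ULN. Raised liver enzymes must return to baseline grade, and ECOG status alone can block the start.
- The direction therefore depends on the mix of non-starters, and the case in which all of them have the event is only an upper bound.

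Nor should a reader infer that harm after TACE goes unwatched. Adverse events are assessed from consent, local serious events go to the monitoring committee, the 6.6 stopping rule covers TACE, and withdrawals are tabulated with reasons. None of this fixes the denominator of the reported rate.

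Finally, the endpoint is secondary and descriptive, and even the 12-point shift to 52% lies inside the exact 95% interval for 16/40 (24.9% to 56.7%). That limits the weight of the point. A systematic shift is still not made harmless by being smaller than the sampling error.

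**Conclusion.** The point holds in a conditional form. Section 8.2 as written limits the safety set to LEE011 starters, 3.1 and 12.1 use a broader but undefined term, and no other section says which governs. If 8.2 is followed, the toxicity rate for the combined regimen is conditional on starting LEE011, and for patients kept from starting by toxicity the expected effect is understatement.

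The overall sign and size cannot be derived from the documents. Under the assumptions of 40 starters, a 40% rate and 5% to 20% non-starters, the all-TACE rate lies between 3 and 12 points above the 8.2 rate if every non-starter has the event, and between 2 and 8 points below it if none does. The contrast also assumes that *therapy* includes TACE.

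This should be settled before the safety data are analysed. It does not touch the PFS design.

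**What to change.** - Put one definition in 3.1, 8.2 and 12.1: the safety set for the combined regimen is all patients who receive on-study TACE.
- Report beside it a labelled subset of patients who took LEE011 at least once. This preserves the 8.2 analysis and is the right set for LEE011-specific toxicity.
- List TACE-treated patients who never start LEE011, with the reason for each, and show RB-negative screen failures given TACE separately.
- State an adverse-event reporting window anchored to TACE for patients who never take LEE011, and reconcile the differing windows in 3.1, Table 7.1 and 12.1.

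The cost is some rewording, an extra column and a short listing in the safety tables, and adverse-event collection for non-starters over the stated window. The reported toxicity rate may look slightly less favourable. Sample size, alpha and power do not change.
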